## **2.6 Visit 5 (week 1)**

Visit 5 will occur 1 week after Visit 4.

The following procedures should be done in the order shown:

- Measure blood pressure and pulse
- Measure orthostatic blood pressure and pulse
- Draw a blood sample and send to the central laboratory

- Take urine sample from the patient and send to central laboratory
- Do a urine pregnancy test (only applicable to women of childbearing potential)
- Measure patient's weight
- After blood pressure and weight measurements, and blood and urine sampling, patient should take investigational product along with other medications. Patient should have a breakfast within 30 minutes after taking medications.
- Review patient's diary for glucometer values/hypoglycaemic events and insulin dose (if applicable) and dispense new diary
- If applicable, calculate and record mean total daily insulin dose based on patient's diary
- Collect and document AEs and SAEs and fill in event forms when applicable
- Document concomitant medications; for anti-hyperglycaemic, anti-hypertensive, lipid lowering and anti-platelet medications daily dose should be recorded in eCRF
- Perform brief physical examination (see details at Visit 2)
- Give diet and lifestyle advice
- Schedule Visit 6 four weeks after Visit 4, ask the patient to be fasting and give instructions what concomitant medications are allowed to take in the morning of the next visit
- Complete eCRF within 72 hours.

## **2.7 Visit 6 (week 4)**

Visit 6 will occur 4 weeks after Visit 4.

The following procedures should be done in the order shown:

- Measure blood pressure and pulse
- Measure orthostatic blood pressure and pulse
- Draw a blood sample and send to the central laboratory
- Take urine sample from the patient and send to central laboratory
- Do a urine pregnancy test (only applicable to women of childbearing potential)

- Measure patient's weight
- After blood pressure and weight measurements, and blood and urine sampling, patient should take investigational product along with other medications. Patient should have a breakfast within 30 minutes after taking medications
- Review patient's diary for glucometer values/hypoglycaemic events and insulin dose (if applicable) and dispense new diary
- If applicable, calculate and record mean total daily insulin dose based on patient's diary
- Check drug accountability
- Collect and document AEs and SAEs and fill in event forms when applicable
- Document concomitant medications; for anti-hyperglycaemic, anti-hypertensive, lipid lowering and anti-platelet medications daily dose should be recorded in eCRF
- Perform brief physical examination (see details at Visit 2)
- Do a re-supply of IP (Dapagliflozin/placebo) in IWRS/IVRS
- Do kit verification transaction in the IWRS/IVRS and dispense IP
- Give diet and lifestyle advice
- Schedule Visit 7 eight weeks after Visit 4, ask the patient to be fasting and give instructions what concomitant medications are allowed to take in the morning of the next visit
- Complete eCRF within 72 hours.

## **2.8 Visit 7 (week 8)**

Visit 7 will occur 8 weeks after Visit 4.

The following procedures should be done in the order shown:

- Ask patient to complete EQ-5D questionnaire
- Do blood pressure and pulse examination
- Do orthostatic blood pressure and pulse examination
- Draw a blood sample and send to the central laboratory

- Take urine sample from the patient and send to central laboratory
- Do a urine pregnancy test (only applicable to women of childbearing potential)
- Measure patient's weight
- After blood pressure and weight measurements, and blood and urine sampling, patient should take investigational product along with other medications. Patient should have breakfast within 30 minutes from taking medications.
- Review patient's diary for glucometer values/hypoglycaemic events and insulin dose (if applicable) and dispense new diary
- If applicable, calculate and record mean total daily insulin dose based on patient's diary
- Check drug accountability
- Collect and document AEs and SAEs and fill in event forms when applicable
- Document concomitant medications; for anti-hyperglycaemic, anti-hypertensive, lipid lowering and anti-platelet medications daily dose should be recorded in eCRF
- Perform brief physical examination (see details at Visit 2)
- Do a re-supply of IP (dapagliflozin/placebo) in IWRS/IVRS
- Do kit verification transaction in the IWRS/IVRS and dispense IP
- Give diet and lifestyle advice
- Schedule Visit 8 sixteen weeks after Visit 4, ask the patient to be fasting and give instructions what concomitant medications are allowed to take in the morning of the next visit
- Complete eCRF within 72 hours.

## **2.9 Visit 8 (week 16)**

Visit 8 will occur 16 weeks after Visit 4.

The following procedures should be done in the order shown:

- Do blood pressure and pulse examination
- Draw a blood sample and send to the central laboratory

- Take urine sample from the patient and send to central laboratory
- Do a urine pregnancy test (only applicable to women of childbearing potential)
- Measure patient's weight
- After blood pressure and weight measurements, and blood and urine sampling, patient should take investigational product along with other medications. Patient should have breakfast within 30 minutes from taking medications.
- Review patient's diary for glucometer values/hypoglycaemic events and insulin dose (if applicable) and dispense new diary
- If applicable, calculate and record mean total daily insulin dose based on patient's diary
- Check drug accountability
- Collect and document AEs and SAEs and fill in event forms when applicable
- Document concomitant medications; for anti-hyperglycaemic, anti-hypertensive, lipid lowering and anti-platelet medications daily dose should be recorded in eCRF
- Perform brief physical examination (see details at Visit 2)
- Do a re-supply of IP (dapagliflozin/placebo) in IWRS/IVRS
- Do kit verification transaction in the IWRS/IVRS and dispense IP
- Give diet and lifestyle advice
- Schedule Visit 9 twenty four weeks after Visit 4, ask the patient to be fasting and give instructions what concomitant medications are allowed to take in the morning of the next visit
- Complete eCRF within 72 hours.

## **2.10 Visit 9 (week 24)**

Visit 9 will occur 24 weeks after Visit 4.

The following procedures should be done in the order shown:

- Ask patient to complete EQ-5D questionnaire
- Do blood pressure and pulse examination

- Do orthostatic blood pressure and pulse examination
- Draw a blood sample and send to the central laboratory
- Take urine sample from the patient and send to central laboratory
- Do a urine pregnancy test (only applicable to women of childbearing potential)
- Measure patient's weight
- Do a 12-lead ECG
- After blood pressure and weight measurements, and blood and urine sampling, patient should take investigational product along with other medications. Patient should have breakfast within 30 minutes from taking medications.
- Review patient's diary for glucometer values/hypoglycaemic events and insulin dose (if applicable) and dispense new diary
- If applicable, calculate and record mean total daily insulin dose based on patient's diary
- Check drug accountability
- Collect and document AEs and SAEs and fill in event forms when applicable
- Document concomitant medications; for anti-hyperglycaemic, anti-hypertensive, lipid lowering and anti-platelet medications daily dose should be recorded in eCRF
- Do a complete physical examination
- Do a re-supply of IP (dapagliflozin/placebo) in IWRS/IVRS
- Do kit verification transaction in the IWRS/IVRS and dispense IP
- Give diet and lifestyle advice
- Schedule Visit 10 twenty eight weeks after Visit 4, ask the patient to be fasting and give instructions what concomitant medications are allowed to take in the morning of the next visit
- Complete eCRF within 72 hours.

## **2.11 Visit 10 (week 28)**

Visit 10 will occur 28 weeks after Visit 4.

The following procedures should be done in the order shown:

- Do blood pressure and pulse examination
- Draw a blood sample and send to the central laboratory
- Take urine sample from the patient and send to central laboratory
- Do a urine pregnancy test (only applicable to women of childbearing potential)
- Measure patient's weight
- After blood pressure and weight measurements, and blood and urine sampling, patient should take investigational product along with other medications. Patient should have breakfast within 30 minutes from taking medications.
- Review patient's diary for glucometer values/hypoglycaemic events and insulin dose (if applicable) and dispense new diary
- If applicable, calculate and record mean total daily insulin dose based on patient's diary
- Check drug accountability
- Collect and document AEs and SAEs and fill in event forms when applicable
- Document concomitant medications; for anti-hyperglycaemic, anti-hypertensive, lipid lowering and anti-platelet medications daily dose should be recorded in eCRF
- Perform brief physical examination (see details at Visit 2)
- Do a re-supply of IP (dapagliflozin/placebo) in IWRS/IVRS
- Do kit verification transaction in the IWRS/IVRS and dispense IP
- Give diet and lifestyle advice
- Schedule Visit 11 thirty six weeks after Visit 4, ask the patient to be fasting and give instructions what concomitant medications are allowed to take in the morning of the next visit
- Complete eCRF within 72 hours.

## **2.12 Visit 11 (week 36)**

Visit 11 will occur 36 weeks after Visit 4.

The following procedures should be done in the order shown:

- Do blood pressure and pulse examination
- Draw a blood sample and send to the central laboratory
- Take urine sample from the patient and send to central laboratory
- Do a urine pregnancy test (only applicable to women of childbearing potential)
- Measure patient's weight
- After blood pressure and weight measurements, and blood and urine sampling, patient should take investigational product along with other medications. Patient should have breakfast within 30 minutes from taking medications.
- Review patient's diary for glucometer values/hypoglycaemic events and insulin dose (if applicable) and dispense new diary
- If applicable, calculate and record mean total daily insulin dose based on patient's diary
- Check drug accountability
- Collect and document AEs and SAEs and fill in event forms when applicable
- Document concomitant medications; for anti-hyperglycaemic, anti-hypertensive, lipid lowering and anti-platelet medications daily dose should be recorded in eCRF
- Perform brief physical examination (see details at Visit 2)
- Do a re-supply of IP (dapagliflozin/placebo) in IWRS/IVRS
- Do kit verification transaction in the IWRS/IVRS and dispense IP
- Give diet and lifestyle advice
- Schedule Visit 12 forty four weeks after Visit 4, ask the patient to be fasting and give instructions what concomitant medications are allowed to take in the morning of the next visit
- Complete eCRF within 72 hours.

### **2.13 Visit 12 (week 44)**

Visit 12 will occur 44 weeks after Visit 4.

The following procedures should be done in the order shown:

- Do blood pressure and pulse examination
- Do orthostatic blood pressure and pulse examination
- Draw a blood sample and send to the central laboratory
- Take urine sample from the patient and send to central laboratory
- Do a urine pregnancy test (only applicable to women of childbearing potential)
- Measure patient's weight
- After blood pressure and weight measurements, and blood and urine sampling, patient should take investigational product along with other medications. Patient should have breakfast within 30 minutes from taking medications.
- Review patient's diary for glucometer values/hypoglycaemic events and insulin dose (if applicable) and dispense new diary
- If applicable, calculate and record mean total daily insulin dose based on patient's diary
- Check drug accountability
- Collect and document AEs and SAEs and fill in event forms when applicable
- Document concomitant medications; for anti-hyperglycaemic, anti-hypertensive, lipid lowering and anti-platelet medications daily dose should be recorded in eCRF
- Perform brief physical examination
- Do a re-supply of IP (dapagliflozin/placebo) in IWRS/IVRS
- Do kit verification transaction in the IWRS/IVRS and dispense IP
- Give diet and lifestyle advice
- Schedule Visit 13 fifty two weeks after Visit 4, ask the patient to be fasting and give instructions what concomitant medications are allowed to take in the morning of the next visit
- Complete eCRF within 72 hours.

## **2.14 Visit 13**

Visit 13 will occur 52 week after Visit 4.

The following procedures should be done in the order shown:

- Ask patient to complete EQ-5D questionnaire
- Do blood pressure and pulse examination
- Do orthostatic blood pressure and pulse examination
- Draw a blood sample and send to the central laboratory
- Take urine sample from the patient and send to central laboratory
- Do a urine pregnancy test (only applicable to women of childbearing potential)
- Measure patient's weight
- Do a 12-lead ECG
- After blood pressure and weight measurements, and blood and urine sampling, patient should take investigational product along with other medications. Patient should have breakfast within 30 minutes from taking medications.
- Review patient's diary for glucometer values/hypoglycaemic events and insulin dose (if applicable)
- If applicable, calculate and record mean total daily insulin dose based on patient's diary
- Check drug accountability. Collect from patient all used and unused bottles with study drug.
- Collect and document AEs and SAEs and fill in event forms when applicable
- Document concomitant medications; for anti-hyperglycaemic, anti-hypertensive, lipid lowering and anti-platelet medications daily dose should be recorded in eCRF
- Do a complete physical examination
- Do a re-supply of IP (dapagliflozin/placebo) in IWRS/IVRS
- Do kit verification transaction in the IWRS/IVRS and dispense IP
- Give diet and lifestyle advice

- Schedule Visit 14 sixty five weeks after Visit 4, ask the patient to be fasting and give instructions what concomitant medications are allowed to take in the morning of the next visit
- Complete eCRF within 72 hours

## **2.15 Visit 14**

Visit 14 will occur 65 weeks after Visit 4.

The following procedures should be done in the order shown:

- Do blood pressure and pulse examination
- Draw a blood sample and send to the central laboratory
- Take urine sample from the patient and send to central laboratory
- Do a urine pregnancy test (only applicable to women of childbearing potential)
- Measure patient's weight
- After blood pressure and weight measurements, and blood and urine sampling, patient should take investigational product along with other medications. Patient should have breakfast within 30 minutes from taking medications.
- Review patient's diary for glucometer values/hypoglycaemic events and insulin dose (if applicable) and dispense new diary
- If applicable, calculate and record mean total daily insulin dose based on patient's diary
- Check drug accountability
- Collect and document AEs and SAEs and fill in event forms when applicable
- Document concomitant medications; for anti-hyperglycaemic, anti-hypertensive, lipid lowering and anti-platelet medications daily dose should be recorded in eCRF
- Perform brief physical examination (see details at Visit 2)
- Do a re-supply of IP (dapagliflozin/placebo) in IWRS/IVRS
- Do kit verification transaction in the IWRS/IVRS and dispense IP
- Give diet and lifestyle advice

- Schedule Visit 15 seventy eight weeks after Visit 4, ask the patient to be fasting and give instructions what concomitant medications are allowed to take in the morning of the next visit
- Complete eCRF within 72 hours.

## **2.16 Visit 15**

Visit 15 will occur 78 week after Visit 4.

The following procedures should be done in the order shown:

- Ask patient to complete EQ-5D questionnaire
- Do blood pressure and pulse examination
- Do orthostatic blood pressure and pulse examination
- Draw a blood sample and send to the central laboratory
- Take urine sample from the patient and send to central laboratory
- Do a urine pregnancy test (only applicable to women of childbearing potential)
- Measure patient's weight
- Do a 12-lead ECG
- After blood pressure and weight measurements, and blood and urine sampling, patient should take investigational product along with other medications. Patient should have breakfast within 30 minutes from taking medications.
- Review patient's diary for glucometer values/hypoglycaemic events and insulin dose (if applicable)
- If applicable, calculate and record mean total daily insulin dose based on patient's diary
- Check drug accountability. Collect from patient all used and unused bottles with study drug.
- Collect and document AEs and SAEs and fill in event forms when applicable
- Document concomitant medications; for anti-hyperglycaemic, anti-hypertensive, lipid lowering and anti-platelet medications daily dose should be recorded in eCRF
- Do a complete physical examination

- Do a re-supply of IP (dapagliflozin/placebo) in IWRS/IVRS
- Do kit verification transaction in the IWRS/IVRS and dispense IP
- Give diet and lifestyle advice
- Schedule Visit 16 ninety one weeks after Visit 4, ask the patient to be fasting and give instructions what concomitant medications are allowed to take in the morning of the next visit
- Complete eCRF within 72 hours

## **2.17 Visit 16**

Visit 16 will occur 91 weeks after Visit 4.

The following procedures should be done in the order shown:

- Do blood pressure and pulse examination
- Draw a blood sample and send to the central laboratory
- Take urine sample from the patient and send to central laboratory
- Do a urine pregnancy test (only applicable to women of childbearing potential)
- Measure patient's weight
- After blood pressure and weight measurements, and blood and urine sampling, patient should take investigational product along with other medications. Patient should have breakfast within 30 minutes from taking medications.
- Review patient's diary for glucometer values/hypoglycaemic events and insulin dose (if applicable) and dispense new diary
- If applicable, calculate and record mean total daily insulin dose based on patient's diary
- Check drug accountability
- Collect and document AEs and SAEs and fill in event forms when applicable
- Document concomitant medications; for anti-hyperglycaemic, anti-hypertensive, lipid lowering and anti-platelet medications daily dose should be recorded in eCRF
- Perform brief physical examination (see details at Visit 2)

- Do a re-supply of IP (dapagliflozin/placebo) in IWRS/IVRS
- Do kit verification transaction in the IWRS/IVRS and dispense IP
- Give diet and lifestyle advice
- Schedule Visit 17 one hundred and four weeks after Visit 4, ask the patient to be fasting and give instructions what concomitant medications are allowed to take in the morning of the next visit
- Complete eCRF within 72 hours.

## **2.18 Visit 17 – End of Treatment Visit (week 104)**

Visit 17 will occur 104 weeks after Visit 4.

Patients who prematurely discontinue study treatment permanently should return and complete procedures described for End of Treatment Visit as soon as possible after last intake of Investigational Product.

The following procedures should be done in the order shown:

- Ask patient to complete EQ-5D questionnaire
- Do blood pressure and pulse examination
- Do orthostatic blood pressure and pulse examination
- Draw a blood sample and send to the central laboratory
- Take urine sample from the patient and send to central laboratory
- Do a urine pregnancy test (only applicable to women of childbearing potential)
- Measure patient's weight
- Do a 12-lead ECG
- After blood pressure and weight measurements, and blood and urine sampling, patient should take their medications. Patient should have breakfast within 30 minutes from taking medications.
- Review patient's diary for glucometer values/hypoglycaemic events and insulin dose (if applicable)
- If applicable, calculate and record mean total daily insulin dose based on patient's diary

- Check drug accountability. Collect from patient all used and unused bottles with study drug.
- Collect and document AEs and SAEs and fill in event forms when applicable
- Document concomitant medications; for anti-hyperglycaemic, anti-hypertensive, lipid lowering and anti-platelet medications daily dose should be recorded in eCRF
- Do a complete physical examination
- Give diet and lifestyle advice
- Schedule Visit 18 three weeks after Visit 17
- Complete eCRF within 72 hours.

### **2.19 Visit 18 – Follow-up Visit (3 weeks after last intake of investigational product)**

Visit 18 will occur 3 weeks after last intake of investigational product, both for patients who completed study treatment according to study schedule and for patients who prematurely discontinued study treatment.

The following procedures should be done in the order shown:

- Do blood pressure and pulse examination
- Draw a blood sample and send to the central laboratory
- Take urine sample from the patient and send to central laboratory
- Do a urine pregnancy test (only applicable to women of childbearing potential)
- Measure patient's weight
- After blood pressure and weight measurements, and blood and urine sampling, patient should take their medications. Patient should have breakfast within 30 minutes from taking medications.
- Collect and document AEs and SAEs and fill in event forms when applicable
- Perform brief physical examination (see details at Visit 2)
- Give diet and lifestyle advice
- Complete eCRF within 72 hours.

## 2.20 Rescue Visit

If the patient meets rescue criteria based on self-monitored glucose values between Visits 4 and 17, the patient should return to the study site within 1 week. Unscheduled visit will be performed to verify FPG value by the central laboratory. When a laboratory result indicates that a patient meets the rescue criteria, a Rescue Visit should be scheduled within 5 workdays. Glycaemic Rescue Criteria for initiation of rescue therapy are in Section 5.6.2 of the CSP.

The following procedures should be done in the order shown:

- Do blood pressure and pulse examination
- Draw a blood sample and send to the central laboratory
- Take urine sample from the patient and send to central laboratory
- Do a urine pregnancy test (only applicable to women of childbearing potential)
- Measure patient's weight
- After blood pressure and weight measurements, and blood and urine sampling, patient should take investigational product along with other medications. Patient should have breakfast within 30 minutes from taking medications.
- Review patient's diary for glucometer values/hypoglycaemic events and insulin dose (if applicable)
- Collect and document AEs and SAEs and fill in event forms when applicable
- Document concomitant medications; for anti-hyperglycaemic, anti-hypertensive, lipid lowering and anti-platelet medications daily dose should be recorded in eCRF
- Do a complete physical examination
- Give diet and lifestyle advice
- Complete eCRF within 72 hours.

---

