### **5.6.2 Randomised treatment period: Initiation of Rescue Therapy**

#### **5.6.2.1 Glycaemic rescue therapy during the randomised treatment period**

The dose of anti-hyperglycaemic medications (oral anti-diabetic drugs and/or insulin) should not be increased or decreased between randomisation and week 104 (Visits 4 to 17) unless rescue criteria or a definition of hypoglycaemia (see Section 5.6.2.3) are met. The need for initiation of rescue therapy will be assessed based on FPG during the 24-week double blind treatment period, and based on HbA1c during the 28-week and 52-week site and patient

blinded extension periods. Numeric criteria are listed in [Table 6](#). Glycaemic rescue is not a reason for discontinuation in this study.

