**Table 6 Glycaemic Rescue Criteria (24-week double blind treatment period)**

Period	Central Laboratory FPG
From week 0 (Visit 4) to week 4 (Visit 6) including day of Visit 6	FPG >270 mg/dL (15.0 mmol/l)
From week 4 (Visit 6) to week 8 (Visit 7) including day of Visit 7	FPG >240 mg/dL (13.2 mmol/l)
From week 8 (Visit 7) to week 24 (Visit 9) including day of Visit 9	FPG >200 mg/dL (11.1 mmol/l)

If self-monitored FPG is above the upper limit defined for each period as described in [Table 6](#), the patient should repeat the FPG on the same day. If the second result is also above the upper limit defined for each period as described in [Table 6](#), the patient should contact the study centre and will be scheduled for a central laboratory FPG measurement within one week. If the FPG result of the central laboratory is above the upper limit of the treatment period as described in [Table 6](#), the rescue criterion is met and a Rescue Visit will be scheduled within 5 working days to adjust the anti-hyperglycaemic therapy.

**Table 7 Glycaemic Rescue Criterion (28-week site- and patient-blinded treatment period I and 52-week site- and patient-blinded extension period II)**

Period	Central Laboratory HbA1c
From week 24 (Visit 9) to week 52 (Visit 13) including day of Visit 13.	Central Laboratory HbA1c >8.0% (repeated and confirmed)
From week 52 (Visit 13) to week 65 (Visit 14) including day of Visit 14.	Central Laboratory HbA1c >7.5% (repeated and confirmed)
From week 65 (Visit 14) to week 104 (Visit 17) excluding day of Visit 17	Central Laboratory HbA1c >7.0% (repeated and confirmed)

From week 24 (Visit 9) to week 104 (Visit 17), if self-monitored FPG is above 200 mg/dL, the patient should repeat the FPG on the same day. If the second result is also above 200 mg/dL, the patient should contact the study centre and will be scheduled for a central laboratory HbA1c measurement within one week.

Investigators are blinded to patients' HbA1c results throughout the study. However, after Visit 9 (week 24), during the 28-week and the 52-week site- and patient- blinded extension periods, a different glycaemic rescue criterion has been defined for the safety of the patients. From week 24 (Visit 9) to week 52 (Visit 13) patients with a central laboratory HbA1c value

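### Appendix E 2.20 names central FPG as the check on self-monitored glucose flags through Visit 17, but after Visit 9 Section 5.6.2.1 and Table 7 require central HbA1c (minor error in an operative instruction)

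*Supplement*

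**What the plan says.** **Appendix E, Section 2.20** opens with "If the patient meets rescue criteria based on self-monitored glucose values between Visits 4 and 17". The patient is then to return within a week, and the check at that return is: "Unscheduled visit will be performed to verify FPG value by the central laboratory". No other test is named and nothing changes at Visit 9. The section gives no threshold of its own. It adds: "Glycaemic Rescue Criteria for initiation of rescue therapy are in Section 5.6.2 of the CSP".

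**Section 5.6.2.1** splits the rule at week 24. Rescue is assessed "based on FPG during the 24-week double blind treatment period, and based on HbA1c during the 28-week and 52-week site and patient"-blinded extension periods. The last FPG row of Table 6 runs "From week 8 (Visit 7) to week 24 (Visit 9) including day of Visit 9", with a limit of 200 mg/dL. Table 7 then gives HbA1c limits only, each to be repeated and confirmed: above 8.0% to week 52, above 7.5% to week 65 and above 7.0% after that. Its last row reads "From week 65 (Visit 14) to week 104 (Visit 17) excluding day of Visit 17".

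For self-monitoring from Visit 9 to Visit 17, Section 5.6.2.1 says "if self-monitored FPG is above 200 mg/dL, the patient should repeat the FPG on the same day". If the second value is also above that level, "the patient should contact the study centre and will be scheduled for a central laboratory HbA1c measurement within one week".

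**The concern.** Two current parts of the protocol give a site different tests for the same event after Visit 9. Sections 3.1.1 and 6.2 send sites to Appendix E for visit assessments and their order, so 2.20 is an instruction that staff would act on. A site that follows it in the extension draws an FPG sample for which no rescue limit exists. The HbA1c that decides rescue is then not drawn at that visit.

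The numerical flag does not help the site notice the change. The last Table 6 limit and the later self-monitoring threshold are both 200 mg/dL, so at Visit 9 the flag looks the same and only the test differs.

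What is at stake is the timeliness of a hyperglycaemia safeguard during the extension, in patients whom the protocol regards as high risk.

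**Working it through.** No stated figure is in dispute. The check compares the texts and then counts visits on the schedule.

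**1. Side by side**

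| Period | Appendix E 2.20 | Section 5.6.2.1 | Rescue criterion |
|---|---|---|---|
| Visit 4 to day of Visit 9 | central FPG | central FPG within one week | Table 6, FPG |
| After Visit 9, to Visit 17 | central FPG | central HbA1c within one week | Table 7, HbA1c, repeated and confirmed; day of Visit 17 excluded |

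The first row agrees. The second conflicts, and no FPG rescue limit exists there.

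**2. How the conflict arose.** The amendment moved the end point in 2.20 from Visit 13 to Visit 17 and added the HbA1c paragraph to 5.6.2.1. It left the FPG sentence in 2.20 as it was. The conflict stands in the current text, not only in the amendment log.

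**3. Rescue routes that do not depend on 2.20.** On-treatment visits after week 24 (Table 3) fall at weeks 28, 36, 44, 52, 65, 78, 91 and 104, which is 8 visits. Table 8 schedules HbA1c at all of them. Table 7 excludes the day of Visit 17, so the HbA1c at Visits 10 to 16 can trigger rescue: 8 − 1 = 7 of 8. At those visits the central laboratory itself asks for the repeat and then instructs rescue, however a site reads 2.20.

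**4. Longest wait if a site takes the test from 2.20.** The gaps between visits from week 24 are

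28−24 = 4; 36−28 = 8; 44−36 = 8; 52−44 = 8; 65−52 = 13; 78−65 = 13; 91−78 = 13; 104−91 = 13.

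Sum: 4 + 3×8 + 4×13 = 80 weeks, the full extension.

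| Flag arises in weeks | Longest wait for a scheduled HbA1c that can trigger rescue | Section 5.6.2.1 |
|---|---|---|
| 24–28 | 4 weeks | 1 week |
| 28–52 | 8 weeks | 1 week |
| 52–91 | 13 weeks | 1 week |
| 91–104 | none scheduled | 1 week |

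These are calendar upper bounds before visit windows. They do not count patients or missed rescues.

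**5. The last row.** A Visit 16 HbA1c above 7.0% still leads to repeat and rescue. The row therefore concerns mainly patients not above 7.0% at week 91 who later record two same-day values above 200 mg/dL.

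**6. Reach into the analyses.** Both primary and all key secondary endpoints are measured at week 24 or earlier, where 2.20 and 5.6.2.1 agree. Section 12.2.5 treats analyses of data up to weeks 52 and 104 as supplemental.

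**The case against.** The strongest case is that the governing text is correct and identified. Sections 3.1.1.4, 3.1.1.5 and 6.4.9.1 assign both the rescue criteria and the procedures that go with them to Section 5.6.2, and 2.20 refers there too. Because 2.20 has no threshold, a site must normally open 5.6.2.1 to recognise a flag after Visit 9, and there the 200 mg/dL rule and the HbA1c order stand in one short paragraph. The FPG sentence does not forbid HbA1c, and the sentence after it speaks only of a laboratory result. The exclusion of the day of Visit 17 belongs to Table 7, not to 2.20. Study drug also stops at that visit, after which treatment is at the investigator's judgement.

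Most of this stands, and it is why the point is minor. It does not remove the conflict. The pointer in 2.20 covers the criteria, while 2.20 states the verifying test itself, and after Visit 9 that test is the wrong one. Table 8 lists HbA1c at the Rescue Visit, but that visit follows a criterion already met, so it does not supply the missing check.

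A reader might infer that extension patients lack a working glycaemic rescue route for 80 weeks, or that rescues would be missed in number. The documents do not support either. Seven scheduled HbA1c visits trigger rescue independently, and nothing in the documents says how many sites would take the test from 2.20 or how many patients would raise a flag.

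**Conclusion.** The point holds as a minor but real error in an operative safety instruction. After Visit 9, Appendix E 2.20 names a test that cannot trigger rescue and that contradicts the one ordered in Section 5.6.2.1.

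The residual risk is a delayed deciding HbA1c. It assumes a site that recognises the flag from 5.6.2.1, or carries the 200 mg/dL limit over from Table 6, and then follows 2.20 for the test. Under that assumption the delay is bounded by the visit spacing in the table above. Only flags after Visit 16 have no later scheduled HbA1c that can lead to rescue. The confirmatory week 24 results do not depend on this.

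**What to change.** Reword the verification sentence in Appendix E 2.20 along these lines:

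> At the unscheduled visit the central laboratory verifies FPG (up to and including the day of Visit 9; compare with Table 6) or HbA1c (after Visit 9 to Visit 17; within one week of two same-day self-monitored values above 200 mg/dL, as in Section 5.6.2.1; rescue if repeated and confirmed per Table 7, which excludes the day of Visit 17).

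The HbA1c check should run to Visit 17, because Section 5.6.2.1 runs it that far. Only the Table 7 criterion leaves out that day, and ending the check a day sooner would create a new mismatch.

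Separately, and as an editorial matter only, Section 5.6.2.1 could cite Table 7 beside Table 6 where it says where the numeric criteria are found.

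The cost is one or two sentences in the appendix and one table reference. No visit is added; only the sample drawn at the unscheduled visit changes.
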